5.4 Fatigue MID score

The MID score +1 will be assigned if ≥ 10 points increase from baseline in fatigue total score. The MID score -1 will be assigned if ≥ 10 points reduction from baseline in fatigue total score. Otherwise the MID score is 0.

5.5 Growth Velocity

Growth will be assessed by anthropometric measurements of height. Z-scores and percentiles will be calculated using CDC growth chart (Kuczmarski, 2000), and for both historical (up to 2 years) and on study anthropometric measurements for males ≤ 18 years and females ≤ 15 at informed consent of this study.

Growth velocity will be assessed by a model-based approach. A linear regression model for each subject will be built for selected pre-treatment data and post-treatment data:

$$Y_t = \beta_0 + \beta_1 X_t + \varepsilon_i$$

Where Y_t is the standing height (cm) or Z score based on the standing height measured at Time t; X_t is the time when standing height is measured; β_0 is the intercept, β_1 is the slope of the regression model; ε_i is random error term.

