#### 7.5.4.8 Anthropometrics

Growth will be assessed from anthropometric measurements (standing height [or recumbent length, if applicable] and weight) at 12-week intervals beginning at the Baseline visit to Week 24, then every 24 weeks thereafter (or at termination visit). Every effort should be made to collect standing height when appropriate. If unable to collect standing height, sitting height should be collected for that subject. Growth velocity will be calculated and compared with pre-treatment growth velocity when available.

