8 STATISTICAL METHODS OF ANALYSIS

8.1 General Principles

All analysis will be performed based on full analysis set, and summaries will be presented overall and for naïve, IST and rollover subjects separately. The statistical analyses will be reported using summary tables, figures, and data listings. Statistical tests will be 2-sided at the alpha =0.05 significance level. All p-values will be presented as nominal p-values. Continuous variables will be summarized with means, standard deviations, medians, minimums, and maximums. Categorical variables will be summarized by counts and by percentages of subjects in corresponding categories. All raw data obtained from the CRFs as well as any derived data will be included in data listings.

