8.7 Efficacy Analyses

Because the primary objective of this study is to evaluate the long-term safety, the efficacy parameters will not be grouped into primary or secondary categories.

The percent change in uGAG excretion will be analyzed using the generalized estimating equation (GEE) method. Model will include baseline a covariate and visit (in this study) as a factor. The covariance structure within subjects will be assumed to be exchangeable.

Descriptive statistics will be presented by assessment time point for observed and change from baseline for the following other efficacy parameters.

- Biomarkers of inflammation in serum
- 6MWT and the percent predicted 6MWT value
- BOT-2
- 3MSCT
- Pulmonary function testing (eg., FVC, FEV and MVV1)
- Shoulder range of motion (goniometry) in extension and flexion by shoulder and the average of the right and left shoulders.
- Visual acuity
- Fatigue
- MPS HAQ
- CHAQ
- HAQ
- Scoring of impactful clinical problems
- Cardiac ventricular mass

Descriptive statistics will be presented by assessment time point for the following other efficacy parameters.

- MDRI
- Fatigue MID
- Subject/Parent/Caregiver CGI scales
- Hepatosplenomegaly

For growth, anthropometric measurements with z scores and percentiles will be summarized by historical time point and on study visit. For naïve subjects, the slopes of growth velocities will be summarized for pre (historical up to 2 years and baseline data) and post (baseline and post treatment data) treatment periods. For IST subjects, the growth velocities will be calculated for pre-initial UX003 treatment (up to 2 years) and post-initial UX003 treatment. For rollover subjects, the growth velocities will be calculated for pre first treatment in the feeder study (up to 2 years) and post first treatment in the feeder study.

For ICR, whether a positive change, according to the MID criteria, has occurred in the prespecified ICR will be assessed. The percentage of subjects achieving an ICR MID will be calculated for the rollover subjects and presented by assessment time point.

- 8.8 Safety Analyses
- 8.8.1 Adverse Events

The latest Medical Dictionary for Regulatory Activities (MedDRA) will be used to code all AEs to a system organ class (SOC) and preferred term.

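### Pre- and post-treatment growth slopes are summarised separately and unweighted, with no minimum history and no pairing within child, although the protocol intends a pre-post comparison

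*SAP*

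**What the plan says.** **SAP 5.5** sets the model: "A linear regression model for each subject will be built for selected pre-treatment data and post-treatment data". The outcome is standing height in cm or its z-score, and the regressor is time. History may reach back up to 2 years. The age limits (males up to 18, females up to 15 at consent) appear with the z-scores and percentiles; I read them as defining the growth subset.

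**SAP 8.7** gives the use of the slopes. For naïve subjects, "the slopes of growth velocities will be summarized for pre (historical up to 2 years and baseline data) and post" treatment periods, and the post fit also includes baseline. For IST subjects, "the growth velocities will be calculated for pre-initial UX003 treatment (up to 2 years) and post-initial UX003 treatment". For rollover subjects the split is at the first treatment in the feeder study.

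**SAP 8.1** supplies the summary method: "Continuous variables will be summarized with means, standard deviations, medians, minimums, and maximums", overall and separately for naïve, IST and rollover subjects. Its general rule, "Statistical tests will be 2-sided at the alpha =0.05 significance level", is not tied to growth.

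**Protocol 7.5.4.8** states the intention: "Growth velocity will be calculated and compared with pre-treatment growth velocity when available". It schedules heights at baseline, Weeks 12 and 24, and every 24 weeks thereafter. Protocol 7.5.2.1 collects growth history for naïve subjects and for those from non-Ultragenyx studies, but sets no number or spacing of heights. Growth is among the other objectives in both documents.

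**The concern.** The protocol intends a contrast, and the SAP delivers two separate sets of descriptive statistics. Nothing requires the same children in both sets, and history will exist for some children and not others. Nothing stops a slope fitted to two nearly adjacent heights from entering the mean with full weight. For naïve subjects the baseline reading sits in both fits, so an error in it pushes the two slopes in opposite directions. Because the selected data are undefined, the choice of historical heights also stays open in an open-label study. At stake is whether the growth comparison can be read as a change within children, and how much of it is measurement error. The heights needed for a better analysis are already being collected.

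**Working it through.** Neither document gives an SE, SD, power or effect size for growth, so there is no planned figure to reproduce. Every SD below is an assumption.

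**1. Different children in the two means.** Let *m* of *n* children have a pre slope and all *n* have a post slope. Then

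mean post (all) − mean pre (*m*) = mean within-child change (*m*) + [(*n* − *m*)/*n*] × [mean post without history − mean post with history].

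The last term is not a treatment effect. For illustration, if 3 of 12 children lack history and grow 2 cm/yr faster than the rest, it equals 0.25 × 2 = 0.5 cm/yr.

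**2. Unequal precision, equal weight.** The slope SE is SD/√Σ(t − t̄)².

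- Post slope, using the protocol's Weeks 0, 12, 24, 48, 72, 96, 120 and 144: the mean is 64.5 weeks and Σ(t − t̄)² = 19,278 weeks², which is 19,278/52.18² = 7.08 years². At SD 0.7 cm, SE = 0.7/2.66 = 0.26 cm/yr.
- Pre slope from two heights 12 weeks (0.23 year) apart: SE = 0.7 × 1.414/0.23 = 4.3 cm/yr.

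The variance ratio is about 270. One such child among 12 would alone contribute 4.3/12 = 0.36 cm/yr to the SE of the mean (0.15 at SD 0.3 cm, 0.26 at SD 0.5 cm). The share is larger within a single subject type.

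**3. Shared baseline (naïve subjects).** In the post fit, baseline has weight −64.5/19,278 per week, which is −0.175 per year. In a two-height pre fit of span *s* it has weight +1/*s*. In units of SD², the error variance of post minus pre is 2/*s*² + 1/7.08 + 2 × 0.175/*s*, where the last term comes from sharing. For *s* = 2 years this is 0.50 + 0.14 + 0.17 = 0.82, against 0.64 without sharing. The error SE is then √(0.82/0.64) = 1.13 times as large. At *s* = 0.23 year the sharing term is small (1.5 against 37.9).

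**4. What a joint analysis could gain.** Two estimators of the mean change in slope were compared on the same heights:

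- two-stage: SE = √ΣVar(post slope − pre slope)/*n*;
- one model with random intercept, pre slope and change of slope at treatment start: the generalised least squares SE with variances known, which is the best case for that model.

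Assumed: *n* = 12; height error SD 0.3, 0.5 or 1.0 cm; pre-slope SD 2 cm/yr; slope-change SD 0.5, 1 or 2 cm/yr; correlation −0.5; this study's eight heights, with baseline in both fits.

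| Pre-treatment history | Reduction in SE |
|---|---|
| All 2 years | 0-8% |
| All 0.5 year | 3-17% |
| Spans uniform 0.5-2 years | 1-23% (medians) |
| Spans uniform 0.25-2 years | 2-37% (medians) |
| A quarter 0.5 year, rest 2 years | 1-41% |
| A quarter 0.25 year, rest 2 years | 4-66% |

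At error SD 0.5 cm and slope-change SD 1 cm/yr, the SE goes from 0.31 to 0.31 (about 1%) with full histories, from 0.37 to 0.33 (11%) with a quarter at 0.5 year, and from 0.52 to 0.35 (33%) with a quarter at 0.25 year.

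The quarter with the short history carries 28-76% of the variance at 0.5 year and 37-92% at 0.25 year. With equal histories every quarter carries 25%.

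With variances estimated by REML (150 simulated trials per setting, slope-change SD 1 cm/yr, error SD 0.5 / 1.0 cm), the reductions were −1% / 0% with full histories, 11% / 25% with spans uniform 0.25-2 years, and 34% / 51% with a quarter at 0.25 year. Many fits gave convergence or non-positive-definite warnings.

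**The case against.** Growth is one of several other objectives, and its analysis is descriptive: no growth-specific test, SE or interval is planned, so there is no planned inference to improve. The median, minimum and maximum are reported with the mean, so an extreme slope would be visible and would not control the median. Per-subject slopes are a recognised two-stage method. Undefined selection may be where unsuitable histories are meant to be dropped. A random-coefficient model in about 12 children is fragile and assumes straight-line growth with one break. The calculation also omits earlier post-treatment heights that rollover and IST subjects may have, and applies the shared baseline to everyone although the SAP specifies it only for naïve subjects.

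Most of this stands, and it limits the size of the claim. It also rules out two stronger readings. A reader might infer that a few short histories dominate the result, but the documents do not show that any child has a short span; they only fail to exclude one. A reader might also infer that a mixed model would cut the SE by a fixed amount such as 30-40%. That figure cannot be derived from the documents and is one part of a 0-66% range.

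The objection does not answer the missing pairing or the undefined selection. A median of pre slopes and a median of post slopes can still come from different children.

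**Conclusion.** The point holds as a gap in specification. As written, the SAP does not deliver the within-child comparison that the protocol intends: the pre and post means can reflect different children, slopes of very different precision count equally, and naïve subjects' shared baseline adds error to the difference. That much follows from the text, with *unweighted* inferred from the simple summaries in SAP 8.1.

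The loss of precision is conditional. It is negligible if all children have about 2 years of history, and the SE could be more than halved if some histories are short and heights are noisy. The documents do not say which case applies. The need for pairing and for a definition of the selected data does not depend on that answer.

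**What to change.** 1. In SAP 5.5, define the selected data by prespecifying a minimum pre-treatment span and a minimum number of heights. In SAP 8.7, report the within-subject change in slope (cm/yr and z-score/yr) with a 95% CI, only in subjects who have both slopes.
2. Add one linear mixed model of standing height on all eligible subjects pooled, with a change of slope at the first UX003 dose. Include available feeder-study or earlier-treatment heights for rollover and IST subjects. Prespecify a simpler random-effects structure, or precision-weighted slopes, in case it does not converge.
3. Keep the per-subject slopes as a listing.

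The cost is SAP wording and a little more analysis; no new data are needed. Some children will drop out of the paired summary. The model assumes linear growth with one break and may need simplifying at this sample size, so it should support the paired summary and not replace it.

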5.6 Percent predicted Six-Minute Walk Tests

To calculate the percent predicted 6MWT value, the following formulas will be applied (Geiger et al. 2007) for subjects aged <20 years old at informed consent of this study

For Males:
$$X_i = \frac{X_{0i}}{196.72 + (39.81 * Age) - (1.36 * Age^2) + (132.28 * Height)} * 100$$

For Females:
$$X_i = \frac{X_{0i}}{188.61 + (51.50 * Age) - (1.86 * Age^2) + (86.10 * Height)} * 100$$

Where:

 X_i = The percent predicted 6MWT result at time i for subject X

 X_{0i} = The 6MWT (m) result at time i for subject X

To calculate the percent predicted 6MWT value, the following formulas will be applied (Gibbons et al. 2001) for subjects aged ≥ 20 years old 15 at informed consent of this study:

$$X_i = \frac{X_{0i}}{868.8 - (2.99 * Age) + (74.7 * Women)} * 100$$

Where:

 X_i = The percent predicted 6MWT result at time i for subject X X_{0i} = The 6MWT (m) result at time i for subject X The age and height measured at corresponding visit will be used to calculate percent predicted 6MWT value.

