5 DEFINITIONS

5.1 Baseline

Naïve subjects:

• uGAG baseline is defined as the average of all assessments prior to or on the date of the first dose of UX003 in this study. Baseline value for other endpoints is the last non-missing assessment prior to or on the date of the first dose of UX003 in this study.

IST subjects:

- uGAG baseline is the average of all assessments prior to or on the date of the initiation of the initial treatment with UX003.
- Baseline value for other endpoints is the last non-missing assessment prior to or on the date of first dose of UX003 in this study.

Rollover subjects:

- The baseline (efficacy and safety) defined in feeder study will be used for this study.
- 5.2 Fold increase in uGAG above upper normal limit

The fold increase in uGAG above upper limit of normal is the ratio of the uGAG value over the uGAG upper limit of normal. If the ratio is less than 1, then it is set 1.

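### SAP 5.6 keeps late-teen subjects on the under-20 walk-test equation after they turn 20, so percent predicted 6MWT rises with no change in distance (minor)

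*SAP*

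**What the plan says.** SAP 5.6 gives one pair of equations, by sex, "for subjects aged <20 years old at informed consent of this study", and a separate adult equation for those aged 20 or over at the same date. The under-20 equations are quadratic in age and linear in height. The adult equation is linear in age.

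The equation is thus fixed once per subject, but the age put into it is not: "The age and height measured at corresponding visit will be used to calculate percent predicted 6MWT value". Neither document caps the age, re-selects the equation, or mentions subjects who turn 20 on study. Protocol 7.5.4.3 says only that percent predicted is based on published normative data.

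SAP 8.7 lists "6MWT and the percent predicted 6MWT value" among the efficacy parameters summarised descriptively by time point, as observed value and change from baseline. For rollover subjects, SAP 5.1 states: "The baseline (efficacy and safety) defined in feeder study will be used for this study". The schedules of events in both documents continue the 6MWT every 24 weeks to Week 144.

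**The concern.** Percent predicted is meant to take age and body size out of the walk distance. A quadratic in age does this only over the ages it was built for. These quadratics have their maximum in the mid-teens and then fall faster each year. A subject who consents shortly before turning 20 is carried down that slope for almost three more years. The denominator shrinks, and the same walk scores higher at each visit.

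The error favours the drug. It enters a change-from-baseline summary in a small, uncontrolled study, which SAP 8.1 also breaks down into naïve, IST and rollover subjects. Late-teen subjects are foreseeable: the protocol sets no upper age limit and, in 7.4.3, expects paediatric, adolescent and adult subjects.

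**Working it through.** The plan gives no worked percent predicted value, so there is no figure of its own to reproduce. The equations in SAP 5.6 were evaluated directly.

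**Inputs**
- Predicted distance in metres, at age *a* (years) and height *h*, from SAP 5.6:
  - Male: P(a) = 196.72 + 39.81a − 1.36a² + 132.28h
  - Female: P(a) = 188.61 + 51.50a − 1.86a² + 86.10h
- Duration, from SAP 3.2: 144 weeks = 1008 days; 1008/365.25 = 2.76 years.
- Assumptions: *h* is in metres (the SAP gives no unit), height is constant at 1.40 m, and distance is unchanged.

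**Who is affected.** A subject must turn 20 by Week 144, so age at consent lies between 20 − 2.76 = 17.24 and just under 20. Consent at 19.9 gives age 22.66 at Week 144.

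**Shape.** The maximum is at b/(2c):
- Male: 39.81/(2 × 1.36) = 14.6 years
- Female: 51.50/(2 × 1.86) = 13.8 years

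The slope is b − 2ca. At age 20 it is 39.81 − 54.40 = −14.6 m per year (male) and 51.50 − 74.40 = −22.9 m per year (female), and it steepens with age.

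**Consent at 19.9, whole period**
- Male: 635.6 m at 19.9, 585.7 m at 22.66. 635.6/585.7 − 1 = 8.5%.
- Female: 597.4 m at 19.9, 521.1 m at 22.66. 597.4/521.1 − 1 = 14.6%.

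**Part arising after age 20.** This is P(20)/P(age at Week 144) − 1, with P(20) = 634.1 m (male) and 595.2 m (female).

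| Age at consent | Age at Week 144 | Male: P, rise after 20 | Female: P, rise after 20 |
|---|---|---|---|
| 19.9 | 22.66 | 585.7 m, 8.3% | 521.1 m, 14.2% |
| 18.5 | 21.26 | 613.6 m, about 3% | 563.3 m, about 6% |
| 17.5 | 20.26 | 630.2 m, 0.6% | 589.1 m, 1.0% |

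For consent at 19.9, heights of 1.60 to 1.20 m give 7.9% to 8.7% (male) and 13.8% to 14.7% (female).

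**In percentage points.** Take an illustrative constant walk of 300 m and consent at 19.9. The male value goes from 300/634.1 = 47.3% at age 20 to 300/585.7 = 51.2% at Week 144. The female value goes from 300/595.2 = 50.4% to 300/521.1 = 57.6%. One such female among 20 contributing subjects would move the mean by 7.2/20 = 0.36 points.

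**Comparison.** The adult equation for a male gives 868.8 − 2.99 × 20 = 809.0 m at 20 and 801.0 m at 22.66, a drift of about 1%.

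**The case against.** Four points can be made on the other side.

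- **The rule is followed as written.** The limit in SAP 5.6 is age at consent, so visits after 20 are inside the rule, and the documents do not give the upper age of the paediatric reference. This is correct. The argument rests on the SAP's own split at 20 and on how the quadratic behaves beyond it, not on a breach of a published range.
- **The largest figures are a worst case.** This stands. The post-20 rise shrinks quickly with younger consent age, and there may be no subject aged 17 to 19 among the roughly 20 planned.
- **Little depends on the variable.** This stands. It is descriptive and untested, and raw distance is summarised beside it. The MDRI domain in SAP 5.3 uses metres and percentage change in distance. The listings of raw and derived data promised in SAP 8.1 would let a careful reader see the discrepancy.
- **Drift also occurs below 20.** This stands. Between 17.24 and 20 an unchanged walk already gains 4.7% (male) or 8.2% (female) at 1.40 m, and a cap at 20 leaves that in place.

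A reader might also infer a second fault in the opposite direction: a rollover under 20 at feeder baseline but 20 or over at consent here would fall from the paediatric to the adult scale. For a 1.40 m male aged 19.2 and then 20.1, walking 300 m, that would be 300/645 = 46.5% to 300/808.7 = 37.1%. The documents do not support this. SAP 5.6 assigns the equation to the subject and defines the result at each time point, so its plain reading is one equation throughout. On the adult equation the same male scores 300/811.4 = 37.0% and then 37.1%. SAP 5.1 says the feeder baseline is used. It does not say that a percentage computed in the feeder study is carried forward, and that calculation is not in these documents.

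**Conclusion.** The point holds, at minor severity. For subjects aged about 17.2 to under 20 at consent, SAP 5.6 produces a rise in percent predicted 6MWT that reflects age alone. At Week 144 the part arising after age 20 is at most about 8% (male) or 14% (female) in relative terms for consent at 19.9, falling to about 1% or less for consent at 17.5. These figures assume height in metres, constant height of 1.40 m and unchanged distance; heights from 1.20 to 1.60 m do not alter the conclusion.

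The effect is confined to the descriptive summaries of this one parameter, chiefly the change from baseline. It does not reach raw 6MWT distance, the MDRI, uGAG or the safety analyses. The number of subjects affected is unknown and may be zero.

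**What to change.** Amend SAP 5.6 in two sentences:

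1. In the under-20 equations, Age is the smaller of age at the visit and 20.
2. The equation chosen by age at consent to this study applies to every time point of that subject, including a rollover's feeder-study baseline, which is calculated from the feeder distance, age and height.

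With the cap, the constant 300 m walk above ends at 47.3% (male) and 50.4% (female), not 51.2% and 57.6%. The second sentence settles the rollover baseline without relying on how the feeder study computed it.

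Two alternatives are worse. Switching to the adult equation at the 20th birthday would replace the rise with a larger artificial drop, from 47.3% to 300/809.0 = 37.1% for the male. Choosing the equation by age at pre-treatment baseline would put some subjects aged 20 or over at consent onto the paediatric equation. It also does not match SAP 5.1 for IST subjects, whose baseline for this endpoint is the last value on or before first dose in this study.

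The cost is two sentences and about one line of programming, with no new data. Values for a few late-teen subjects become slightly less favourable, and the milder drift below age 20 remains.

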5.7 Anti-rhGUS Antibody Titer Values

Subject sera will be tested using a bridging anti-drug antibody (ADA) ELISA to screen for antibodies to rhGUS. Samples which are positive in the confirmation assay will then be tested in the titer assay giving a titer value, and also be tested with the neutralizing antibody assay (NAb).

5.8 Duration of exposure to UX003

Duration of exposure to UX003 in days in this is defined as: last date of UX003 infusion – first date of UX003 infusion in this study + 14 days.

